5.1.4 Enzalutamide Storage

Enzalutamide study drug is to be handled and stored safely and properly in accordance with the study drug label.

5.1.5 Directions for Administration of Enzalutamide

The daily dose of enzalutamide is 160 mg/day in 4 capsules (40 mg each) given by mouth. Patients should self-administer enzalutamide study drug by mouth once daily, with or without food, starting on day 1. The capsules should be swallowed whole without chewing, dissolving, or opening them. Patients will self-

administer the study drug at home. Patients should not make up missed or vomited doses; dosing should resume on the next calendar day unless otherwise instructed.

5.1.6 Directions for Dose Modification of Enzalutamide

Patients who experience a grade 3 or higher toxicity that is attributed to enzalutamide study drug and cannot be ameliorated by the use of adequate medical intervention may interrupt treatment with enzalutamide. Subsequently, the enzalutamide dosing may be restarted at the original dose (160 mg/day, 4 capsules) or a reduced dose (80 mg/day, 2 capsules). Treatment interruption and re-initiation should be discussed with the principal investigator.

5.1.7 Treatment Compliance

Study drug accountability will be performed to document compliance with the dosing regimen. Patients will be asked to return all bottles of study drug at study visits. Patients who forget to return bottles will be asked to return them at the next study visit.

5.1.8 Drug Inventory and Accountability

Drug inventory and accountability records for the study drugs will be kept by the investigator/pharmacist. Used or unused study drug may be destroyed at the study site according to standard institutional procedures if the sponsor agrees with the procedure, and after drug accountability has been conducted by the sponsor or representative, unless otherwise approved.

5.1.9 Effects of Enzalutamide on Exposure to Other Drugs

Clinical data indicate that enzalutamide is a strong inducer of CYP3A4 and a moderate inducer of CYP2C9 and CYP2C19. Concomitant use of enzalutamide with drugs with a narrow therapeutic index that are metabolized by CYP3A4 (eg, alfentanil, cyclosporine, dihydroergotamine, ergotamine, fentanyl, pimozide, quinidine, sirolimus, tacrolimus), CYP2C9 (eg, phenytoin, warfarin), and CYP2C19 (eg, S-mephenytoin) should be avoided if possible as enzalutamide may decrease their exposure. If coadministration with warfarin cannot be avoided, additional INR monitoring should be conducted.

5.1.10 Drugs That May Affect Exposure to Enzalutamide

5.1.10.1 Drugs That Inhibit or Induce CYP2C8

Coadministration of a strong CYP2C8 inhibitor (eg, gemfibrozil) increased the composite AUC_{0-∞} of enzalutamide plus its active metabolite in healthy volunteers by 2.2-fold; therefore, coadministration of enzalutamide with strong CYP2C8 inhibitors should be avoided if possible. If coadministration of enzalutamide with strong CYP2C8 inhibitors cannot be avoided, the enzalutamide dose should be reduced to 80 mg once daily. If coadministration of the strong inhibitor is discontinued, the enzalutamide dose should be returned to the dose used prior to initiation of the strong CYP2C8 inhibitor.

The effects of CYP2C8 inducers on the PK of enzalutamide have not been evaluated in vivo. Coadministration of enzalutamide with strong or moderate CYP2C8 inducers (eg, rifampin) may alter the plasma exposure of enzalutamide and should be avoided if possible. Selection of a concomitant medication with no or minimal CYP2C8 induction potential is recommended.

5.1.10.2 Drugs That Induce CYP3A4

The effects of CYP3A4 inducers on the PK of enzalutamide have not been evaluated in vivo. Coadministration of enzalutamide with strong CYP3A4 inducers (eg, carbamazepine, phenobarbital, phenytoin, rifabutin, rifampin, rifapentine) may decrease the plasma exposure of enzalutamide and should be avoided if possible. Selection of a concomitant medication with no or minimal CYP3A4 induction potential is recommended. Moderate CYP3A4 inducers (eg, bosentan, efavirenz, etravirine, modafinil, nafcillin) and St. John's Wort may also reduce the plasma exposure of enzalutamide and should be avoided if possible.

5.1.10.3 Precautions Regarding Concomitant Medications

Refer to the following websites for updated lists of CYP inhibitors, inducers, and substrates.

- <http://www.fda.gov/Drugs/DevelopmentApprovalProcess/DevelopmentResources/DrugInteractionsLabeling/ucm093664.htm#potency>
- <http://medicine.iupui.edu/clinpharm/ddis/table.aspx>

5.2 Fulvestrant

Fulvestrant is an ER antagonist indicated for the treatment of postmenopausal women with hormone receptor-positive advanced breast cancer. Unlike the selective ER modulator tamoxifen, which displays mixed antagonist/agonist properties, fulvestrant has no agonist effects. Fulvestrant binds, blocks, and increases degradation of the ER, leading to an inhibition of estrogen signaling. This distinctive mode of action may overcome tumor resistance to previous endocrine agents. The increased degradation of the ER by fulvestrant may also limit cross-talk between growth factor receptor and ER-mediated signaling pathways and thus increase the duration of response observed with fulvestrant treatment.

Per the USPI8, the recommended dose of fulvestrant is 500 mg administered by IM injection on days 1, 15, and 29 and once monthly thereafter. The most common clinically significant adverse reactions occurring in $\geq 5\%$ of patients receiving fulvestrant 500 mg are injection site pain, nausea, bone pain, arthralgia, headache, back pain, fatigue, pain in extremity, hot flush, vomiting, anorexia, asthenia, musculoskeletal pain, cough, dyspnea, and constipation. In addition, \geq grade 1 elevations in AST, ALT or alkaline phosphatase were observed in $> 15\%$ in pooled analysis of fulvestrant trials, with grade 3 to 4 increases observed in 1% to 2% of patients. Clinical data show that fulvestrant does not affect the pharmacokinetics of midazolam (a sensitive CYP3A4 substrate) and rifampin and

enzalutamide (a potent CYP3A4 inducer) had no effect on the pharmacokinetics of fulvestrant.

5.3 Investigational Product Accountability

The Investigator must maintain accurate records (including dates and lot numbers) of all study drug supplies received. All study drug supplies issued to, used by, and returned by each patient must be recorded on a Drug Accountability Log completed by the Investigator or designee. All remaining study supplies, opened or unopened, must be returned to the Sponsor (or designee) at the end of the study or destroyed on site according to the site's standard operating procedures only after study drug accountability has been completed and with approval of the Study Monitor. All records must be made available to the Sponsor (or designee) and appropriate regulatory agencies upon request.

6. STUDY PROCEDURES AND SCHEDULE:

6.1 Study Procedures

Study Phase	Screening	Treatment				Progression	Follow-up
		1	5	9	13 [1]		
Study Week	-4 to -1	1	5	9	13 [1]	varies	varies [10]
Window (Days)	28	n/a	+/- 7	+/- 7	+/- 7	n/a	+/- 7 days
Informed Consent	x						
Eligibility	x						
Medical History	x						
Archived Tissue Collection [2]	x						
Tumor Imaging [3]	x			x			
Physical Exam	x	x	x	x	x	x	
Adverse Events	x	x	x	x	x	x	x
Concomitant Medications	x	x	x	x	x	x	
Study Drug Dispensing [4]		x		x			
Fulvestrant [9]		x	x	x	x		
Tumor Biopsy		x [5]	x			optional	
Hematology, Serum Chemistry [6]	x	x [8]	x	x	x	x	
PT/INR, PTT [11]	x		x			x	
Urine Pregnancy Test [12]	x						
Circulating Tumor Biomarkers	x	x [8]	x	x	x	x	
CTCs [7]	x	x [8]	x	x		x	
Survival & Recurrence Follow-up							x

[1] Continue every 4 weeks until progression.

[2] From primary lesion and/or metastatic sites previously biopsied. If tissue is available, archival blocks from both sites (primary and metastatic) should be collected, however, the top priority is the primary tissue.

[3] Within approximately 28 days before study entry and includes CT with contrast (unless medically contraindicated) of chest, abdomen, and pelvis. Bone assessments as clinically indicated. Thereafter, perform assessments every 8 weeks up to week 49 and then every 12 weeks thereafter until progression is documented per RECIST 1.1 or permanent treatment discontinuation. MRI is acceptable if CT not possible. Use the same testing across time.

[4] Refill every 8 weeks as long as patient remains on active treatment.

[5] Before treatment, but after eligibility determined.

[6] Hematology: hematocrit, hemoglobin, platelet count, red blood cell count, total neutrophils (absolute), white blood cell count with differential. Chemistry: albumin, alkaline phosphatase, ALT (alanine aminotransferase), AST (aspartate transaminase), blood urea nitrogen and creatinine; Ca⁺⁺, Cl⁻, K⁺, Na⁺; glucose (non-fasting), total bilirubin, total CO₂ (bicarbonate), total protein.

[7] CTCs will be collected at all participating sites, coded to remove patient identifiers, and shipped to UCCC and USC for processing as outlined in the lab manual.

[8] Only one sample is needed pretreatment (either during screening or prior to treatment on C1D1).

[9] Given IM on days 1, 15, and 28 (C2D1), and then every 4 weeks as per standard of care (SOC).

[10] 30 days after the last dose of enzalutamide or before initiation of a new antitumor treatment, whichever occurs first. May be done by telephone.

[11] Collected at screening, tumor biopsy time points if clinically required for biopsy, and as required per institutional standard.

[12] If woman of child bearing potential only.

Bold represents non-SOC events.

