2.3 Secondary Objectives

1. To confirm the safety profile of the combination.
2. Response rate (complete and partial response) at 24 weeks, Progression-free survival (PFS) and % of patients remaining free from progression at 12 and 24 weeks.
3. To obtain serial biopsies of breast cancer pretreatment, during treatment and at time of tumor progression in order to determine the extent of AR expression and signaling in breast tissue, to evaluate the effect of enzalutamide on the tumor, and to evaluate the relationship of these effects on clinical outcomes.

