10.2 Sample Size

10.2.1 Determination of Sample Size

The primary outcome is the clinical benefit rate. Assuming the undesirable rate of 10% and desirable rate of 30%, a sample size of 24 provides 89% power to detect this 25% rate difference using an exact binomial test with a one-sided alpha of 0.085. If 5 or more patients show clinical benefit the drug combination warrants further evaluation. During treatment period, patients might withdraw due to toxicity or loss to follow-up before on treatment for 24 weeks. Table below summarize the statistical power and the decision rule for sample size from 24 to 20, a 20% loss in the total sample size, which is the upper bound for loss seen in practice.

Statistical Power	n	Actual Alpha	Reject H0 If R ≥
0.89	24	0.085	5
0.86	23	0.073	5
0.84	22	0.062	5
0.80	21	0.052	5
0.76	20	0.043	5

R is the response as the clinical benefit

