10.4.2 Analysis Methods

10.4.2.1 Summary Statistics

Summary statistics will be used for the primary outcome clinical benefit rate as well as the response rate. Clinical benefit rate is defined as the proportion of subjects with complete response or partial response or stable disease. Response rate is defined as the proportion of subjects with complete response or partial response. 95% exact confidence intervals will be provided. Kaplan-Meier product limit survival plots will be generated and median survival time and associated 95% CI will be estimated, the PFS percentage at 12 and 24 weeks will be calculated. Descriptive statistics will be used to summarize the safety data such as the DLT for both hematologic and non-hematologic toxicity per type and grade, as well as all collected AE data, which will be listed per patient, and cycle. For the biopsy samples, exploratory analyses such as multivariable logistic regression, linear regressions and survival analyses will be required to attempt to classify protein, gene, or TUNEL markers associated with clinical outcomes such as response, clinical benefit and PFS as predictive (of therapeutic impact) or prognostic (of intrinsic tumor

biology). Bio-informatics tools such as unsupervised pathway analysis will also be explored. The following molecular characteristics at baseline will be explored among others: 1) Nuclear to cytoplasmic localization of AR staining. 2) Strength of AR signaling as measured by the expression of downstream AR-regulated genes, which should reflect dependence of the tumor cell on AR function. 3) AR:ER ratio with resistance to anti-estrogen therapy.

The same summary statistics will be used for the response rate and clinical benefit rate. Response rate is defined as the proportion of subjects with complete response or partial response. Clinical benefit rate is defined as the proportion of subjects with complete response or partial response or stable disease. Kaplan-Meier product limit survival plots will be generated and median survival time and associated 95% CI will be estimated for each arm. Combined and separate data for patients with AR+ and AR- BC and those with one prior endocrine therapy and those with more than one prior endocrine therapy for metastatic breast cancer.

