10.5.2.3 Progression Free Survival

For all patients enrolled, PFS will be defined as the time from the first day of enzalutamide treatment (Study Day 1) until documented disease progression or death on study, whichever occurs first. For patients who do not die or experience disease progression on study, PFS will be right censored at the day of the last information available for progression assessment. Kaplan-Meier methods will be used to describe PFS by dose level and overall.

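### Imaging ends at treatment discontinuation and PFS is then censored with no sensitivity analysis, so the secondary PFS, PFS12 and PFS24 estimates may be overstated

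*Combined protocol and SAP*

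**What the plan says.** Four parts of the combined protocol and SAP act together.

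- **Imaging.** Footnote [3] of the schedule in 6.1 asks sites to "perform assessments every 8 weeks up to week 49 and then every 12 weeks thereafter", and this runs "until progression is documented per RECIST 1.1 or permanent treatment discontinuation". A patient who stops treatment without progression has no further scheduled scans.
- **Event and censoring.** Section 10.5.2.3 counts time from the first day of enzalutamide "until documented disease progression or death on study, whichever occurs first". For everyone else, "PFS will be right censored at the day of the last information available for progression assessment". There is no separate rule for stopping because of toxicity or clinical deterioration, or for starting a new antitumor treatment.
- **Estimator.** Section 10.4.2.1 uses Kaplan-Meier and adds that "the PFS percentage at 12 and 24 weeks will be calculated". Section 2.3 lists these among the secondary objectives: "Progression-free survival (PFS) and % of patients remaining free from progression at 12 and 24 weeks".
- **After treatment.** One contact is planned, "30 days after the last dose of enzalutamide or before initiation of a new antitumor treatment, whichever occurs first. May be done by telephone" (6.1, footnote [10]). The survival and recurrence row is marked at that contact. Imaging is not.

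Section 10.2.1 expects early departures: "patients might withdraw due to toxicity or loss to follow-up before on treatment for 24 weeks". It tabulates sample sizes from 24 down to 20. No sensitivity analysis for PFS appears anywhere in the document.

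**The concern.** Kaplan-Meier is unbiased only if censored patients have the same later risk as those still under observation. Here, leaving treatment ends the assessments that could show progression, and the reasons for leaving may be related to prognosis. Section 4.3 allows removal for adverse events or other medical conditions. Section 7.3 allows a patient whose tumor seems to be growing to come off study, with no stated requirement to document progression first. If such patients tend to progress sooner than those who stay, censoring them makes the curve look better than full follow-up would.

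The trial has one arm, so no control group shares the distortion, and PFS24 will be read as an absolute figure. With 24 patients, a few departures can move it visibly. Nothing in the plan would show the reader by how much.

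**Working it through.** **1. The plan's own figures.** The documents give no PFS or PFS24 value, target or power. The only clinical efficacy calculation is the rule of at least 5 patients with clinical benefit (10.2.1). By the exact binomial:

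- n = 24: P(X ≥ 5 | 10%) = 0.0851 and P(X ≥ 5 | 30%) = 0.889. The plan states 0.085 and 0.89.
- n = 20: 0.0432 and 0.762. The plan states 0.043 and 0.76.

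The table reproduces. It concerns clinical benefit rate, and PFS censoring does not enter it.

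**2. Inputs for an illustration.**

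- From the plan: a loss of 4 from 24 patients, 4/24 = 16.7%.
- Assumed: PFS24 of 30% (also 50%) among those still followed, exponential times, departures at a constant rate over 24 weeks, censoring at departure, and a hazard after leaving equal to k times that of patients still followed.

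**3. Formula.** Let L be the cumulative 24-week progression hazard and G the cumulative 24-week departure hazard.

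- L = −ln(0.30) = 1.204.
- G solves G/(G+L) × (1 − e^−(G+L)) = 4/24, so G = 0.325.
- Kaplan-Meier with leavers censored estimates e^−L = 30%, whatever k is.
- PFS24 under full follow-up = e^−(G+L) + [G/(G + L − kL)] × (e^−kL − e^−(G+L)), where e^−(G+L) = 0.217.
- Example, k = 2: 0.217 + [0.325/(0.325 − 1.204)] × (0.090 − 0.217) = 0.217 + 0.047 = 0.264.

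| k | PFS24 if leavers were followed | Kaplan-Meier minus this (points) |
|---|---|---|
| 0.5 | 33.3% | −3.3 |
| 1 | 30.0% | 0 |
| 1.5 | 27.8% | +2.2 |
| 2 | 26.4% | +3.6 |
| 3 | 24.6% | +5.4 |

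A simulation of 400,000 patients per scenario agrees to within 0.1 point.

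**4. Other inputs.**

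- 2 of 24 leaving, PFS24 of 30%: −1.6, 0, +1.1, +1.8 and +2.7 points for the same values of k.
- 4 of 24 leaving, PFS24 of 50%: −2.3, 0, +1.8, +3.3 and +5.4 points.

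**5. Bounds.** These count every leaver as a failure, so they are limits and not estimates of the bias.

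- All 4 leave before any event: 0.30 × 20/24 = 25%, against 30% when they are censored.
- Departures spread over 24 weeks, as in step 3: 21.7%, at most 8.3 points below 30%. This gap is larger because a patient censored late has already passed part of the risk period, and Kaplan-Meier credits that patient with a better chance of reaching week 24.

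**6. A case that can be checked by hand.** Take 24 patients with 6, 5 and 3 progressions at three successive assessments, and 4 patients censored after the first.

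- Kaplan-Meier: (18/24) × (9/14) × (6/9) = 32.1%.
- All 4 counted as failures: 6/24 = 25.0%.
- All 4 progression-free throughout: 10/24 = 41.7%.

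The truth could lie on either side of the Kaplan-Meier figure.

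**The case against.** The strongest reply is that no bias has been shown, and much of it stands.

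- **Direction.** A reader might infer that the rule necessarily inflates PFS. The documents do not support that. It requires a higher later hazard in leavers, which is plausible for clinical worsening but not established for toxicity, and the plan offers no data on either.
- **What is censored, and when.** A reader might also infer that patients are censored at their last scan, or at about day 1 if they leave before the week 9 scan, and that clinical worsening is always censored. Section 10.5.2.3 refers to progression information in general and does not tie documented progression to a RECIST scan. Physical examinations are scheduled every 4 weeks, tumor markers may be followed (6.3.1), and 10.5.2.2 accepts marker-based or descriptive assessment of response in non-measurable disease. Clinical worsening may therefore count as an event. The text leaves this open.
- **Earliest leavers.** Section 10.4.1 limits efficacy analyses to patients with at least 4 weeks of enzalutamide, and 10.4 replaces patients without both biopsies. Section 10.5.2.3 instead speaks of all patients enrolled. Whether very early leavers enter the PFS analysis is unsettled, so a scenario in which all losses come first is an extreme one.
- **Partial capture.** The 30-day contact covers survival and recurrence, so some early events after treatment can be recorded without imaging.
- **Consequence.** PFS is secondary and carries no test.

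These points limit the direction, size and importance of the concern. They do not supply the missing rules, and the uncertainty over clinical progression is itself a reason to specify them before analysis.

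**Conclusion.** The concern holds in conditional form. Imaging ends at discontinuation, patients without an event are censored, departures before week 24 are expected, and no analysis shows how much the result depends on them. PFS, PFS12 and PFS24 may be overstated if leavers do worse later.

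Under the assumed 30% PFS24 and 4 of 24 leaving, the effect is zero at equal hazard, about 2 to 5 points upward for a hazard 1.5 to 3 times higher, and about 3 points downward for half the hazard. The 25% against 30% comparison is a worst case for departures before any event. None of these sizes is an estimate from the trial's documents.

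A reader might go further and infer that the go/no-go decision is compromised. It is not affected by this route: the rule rests on the count of patients with clinical benefit, and how early leavers enter that count is a separate question. This is a worthwhile, inexpensive improvement to a secondary analysis.

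**What to change.** Keep the current PFS analysis. Add to 10.5.2.3 one pre-specified sensitivity analysis in which each of the following, when it occurs before documented progression, is a PFS event on its own date:

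- discontinuation for toxicity;
- discontinuation for clinical deterioration;
- start of a new antitumor treatment.

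State that clinically documented progression counts as an event in this analysis. Report PFS12 and PFS24 from both analyses, with the number censored by reason.

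Use the reasons and dates collected up to the existing 30-day contact. That contact cannot be relied on for later dates, because footnote [10] ends it at 30 days or before new therapy. Later progression or death dates should be used only where the site already knows them.

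**Cost.** One extra analysis and consistent recording of discontinuation reasons and dates, with no added scans and no change to patient management. The sensitivity estimate will look less favourable and will count some non-progressions as events, which is why the two should be reported side by side.

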6.2 Drug Dispensing

An 8 week supply of enzalutamide will be provided to each patient at a time (provided by Astellas/Medivation) and dispensed by the research pharmacy. Additional bottles may be dispensed to accommodate necessary windows for subsequent visits or for accidental wastage.

6.3 Laboratory Procedures/Evaluations

6.3.1 Blood

Routine blood tests (chemistries, hematology) will be obtained every month as clinically indicated. Tumor markers to be followed every 1-2 months as clinically indicated.

Blood for potential pharmacogenomics testing will be obtained at baseline. The white cell pellet required for this sample will be obtained from the baseline plasma vacutainer.

Plasma for tumor related exosomes and other circulating tumor products will be obtained each cycle on day 1 (10 ml).

Blood for circulating tumor cells will be obtained day 1 of cycles 1, 2, and 3 (up to 30ml each time).

Baseline:

- 1 plasma vacutainer (green top, lithium heparin, 10ml)
- 1 serum vacutainer (red top, 10ml)
- 2-3 tubes for CTC sample collection (up to 30ml)

~Week 5:

- 1 plasma vacutainer (green top, lithium heparin, 10ml)
- 2-3 tubes for CTC sample collection (up to 30ml)

~Week 9:

- 1 plasma vacutainer (green top, lithium heparin, 10ml)
- 2-3 tubes for CTC sample collection (up to 30ml)

~Week 13:

- 1 plasma vacutainer (green top, lithium heparin, 10ml)

End of study:

- 1 plasma vacutainer (green top, lithium heparin, 10ml)
- 2-3 tubes for CTC sample collection (up to 30ml)

